### **Fruits**

For this question, please estimate the frequency and quantity of the item in question. Frequency is estimated as: 1-2 times per week, 3-4 times per week, 5-6 times per week, 1 time per day, 2-3 times per day, 4-5 times per day, 6 or more times per day.

Please quantify intake in terms of servings. The following are examples of 1 SERVING of fruit: 1 piece of medium fresh fruit (apple, orange etc); OR 2 pieces of small fresh fruit (apricot, plum etc); 1/2 cup of tinned/frozen fruit (berries, tinned peaches etc); OR 1 handful of dried fruit (raisins, trail mix).

Please choose only one answer for each question.

Do you consume fruits?

- No
- Yes

For fruit, which of the following categories of fruit do you typically consume?

- Apples
- Berries (raspberries, strawberries, blueberries)
- Citrus fruits (orange, grapefruit, clementines)
- Stone fruits (peaches, apricots)
- Tropical fruits (bananas, pineapple)
- Melons (watermelon, honeydew)
- Grapes

How often do you consume a serving of fruit?

- <1 time per week
- 1-2 times per week
- 3-4 times per week
- 5-6 times per week
- 1 time per day
- 2-3 times per day
- 4-5 times per day
- 6 or more times per day

### **Vegetables**

For this question, please estimate the frequency and quantity of the item in question. Frequency is estimated as: 1-2 times per week, 3-4 times per week, 5-6 times per week, 1 time per day, 2-3 times per day, 4-5 times per day, 6 or more times per day.

Please quantify intake in terms of servings. The following are examples of 1 SERVING of vegetables: 1 medium vegetable (potatoe, carrot, yam, etc.); OR 1/2 cup cooked vegetable (broccoli, peas, spinach etc.); OR 1 cup salad).

Please choose only one answer for each question.

Do you consume vegetables?

- No
- Yes

For vegetables, which of the following categories of vegetables do you typically consume?

- Cruciferous vegetables (broccoli, brussel sprouts)
- Leafy greens
- Marrow vegetables (cucumber, zucchini)
- Root vegetables (potatoes, sweet potatoes)
- Stem vegetables (asparagus)

How often do you consume a serving of vegetables?

- <1 time per week
- 1-2 times per week
- 3-4 times per week
- 5-6 times per week
- 1 time per day
- 2-3 times per day
- 4-5 times per day
- 6 or more times per day

### **Legumes**

For this question, please estimate the frequency and quantity of the item in question. Frequency is estimated as: 1-2 times per week, 3-4 times per week, 5-6 times per week, 1 time per day, 2-3 times per day, 4-5 times per day, 6 or more times per day.

Please quantify intake in terms of servings. The following are examples of 1 SERVING of legumes: 3/4 cup cooked lentils (green, red lentils etc.), 3/4 cup cooked beans (kidney beans, white beans, chickpeas, baked beans, split beans, etc.).

Please choose only one answer for each question.

Do you consume legumes or pulses?

- No
- Yes

How often do you consume a serving of legumes?

- <1 time per week
- 1-2 times per week
- 3-4 times per week
- 5-6 times per week
- 1 time per day
- 2-3 times per day
- 4-5 times per day
- 6 or more times per day

### **Cereals & Breads**

For this question, please estimate the frequency and quantity of the item in question. Frequency is estimated as: 1-2 times per week, 3-4 times per week, 5-6 times per week, 1 time per day, 2-3 times per day, 4-5 times per day, 6 or more times per day.

Please quantify intake in terms of servings. The following are examples of 1 SERVING of breads and/or cereals: 1/2 cup cooked oatmeal (or porridge, cream of wheat etc); OR 1/2 cup cereal or muesli; OR 1 slice whole-grain bread; OR 2 slices white bread).

Please choose only one answer for each question.

Do you consume breads and cereals?

- No
- Yes

For bread, do you typically consume white or whole-grain bread?

- White
- Whole grain

How often do you consume a serving of breads and/or cereals?

- <1 time per week
- 1-2 times per week
- 3-4 times per week
- 5-6 times per week

- 1 time per day
- 2-3 times per day
- 4-5 times per day
- 6 or more times per day

### **Rice & Pastas**

For this question, please estimate the frequency and quantity of the item in question. Frequency is estimated as: 1-2 times per week, 3-4 times per week, 5-6 times per week, 1 time per day, 2-3 times per day, 4-5 times per day, 6 or more times per day.

Please quantify intake in terms of servings. The following are examples of 1 SERVING of rice or pasta: 1/2 cup cooked brown rice or whole-wheat pasta (or quinoa etc.); OR 1 cup cooked white rice or regular pasta).

Please choose only one answer for each question.

Do you consume rice and/or pasta?

- No
- Yes

For rice, do you typically consume white, brown rice or rice alternatives (quinoa etc.)?

- White
- Brown
- Quinoa

For pasta, do you typically consume regular or whole-wheat pasta?

- Regular
- Whole-wheat

How often do you consume a serving of rice or pasta (including alternatives such as quinoa etc.)?

- <1 time per week
- 1-2 times per week
- 3-4 times per week
- 5-6 times per week
- 1 time per day
- 2-3 times per day
- 4-5 times per day
- 6 or more times per day

### **Meat & Poultry**

For this question, please estimate the frequency and quantity of the item in question. Frequency is estimated as: 1-2 times per week, 3-4 times per week, 5-6 times per week, 1 time per day, 2-3 times per day, 4-5 times per day, 6 or more times per day.

Please quantify intake in terms of servings. The following are examples of 1 SERVING of meat and/or poultry: 1 3-oz serving; OR 1 chicken breast; OR 1/2 cup ground meat or poultry).

Please choose only one answer for each question.

Do you consume meat and/or poultry?

- No
- Yes

If you consume meat and/or poultry, what is your primary method of cooking?

- Grilling
- Pan or shallow frying
- Deep-frying
- Baking
- Other

How often do you consume a serving of chicken or other poultry (1 chicken breast or equivalent)?

- <1 time per week
- 1-2 times per week
- 3-4 times per week
- 5-6 times per week
- 1 time per day
- 2-3 times per day
- 4-5 times per day
- 6 or more times per day

How often do you consume a serving of pork, beef or other meat (1 3-oz pork chop, 1 5-oz patty, etc.)?

- <1 time per week
- 1-2 times per week
- 3-4 times per week
- 5-6 times per week
- 1 time per day
- 2-3 times per day
- 4-5 times per day
- 6 or more times per day

### **Fish & Shellfish**

For this question, please estimate the frequency and quantity of the item in question. Frequency is estimated as: 1-2 times per week, 3-4 times per week, 5-6 times per week, 1 time per day, 2-3 times per day, 4-5 times per day, 6 or more times per day.

Please quantify intake in terms of servings. The following are examples of 1 SERVING of fish and/or shellfish: 1 3-oz serving of fish; OR 1 4-oz serving of shrimp; OR 3/4-lb cooked lobster or crab).

Please choose only one answer for each question.

Do you consume fish and/or shellfish?

- No
- Yes

If you consume fish and/or shellfish, what is your primary method of cooking?

- Grilling
- Pan or shallow frying
- Deep-frying
- Baking
- Other

How often do you consume a serving of fish and/or shellfish?

- <1 time per week
- 1-2 times per week
- 3-4 times per week
- 5-6 times per week
- 1 time per day
- 2-3 times per day
- 4-5 times per day
- 6 or more times per day

### **Eggs**

For this question, please estimate the frequency and quantity of the item in question. Frequency is estimated as: 1-2 times per week, 3-4 times per week, 5-6 times per week, 1 time per day, 2-3 times per day, 4-5 times per day, 6 or more times per day.

Please quantify intake in terms of servings. The following are examples of 1 SERVING of eggs: 1 egg; OR 3 egg whites; OR 1 cup egg substitute.

Please choose only one answer for each question.

Do you consume eggs?

- No
- Yes

If you consume eggs, do you typically consume whole eggs or egg products (egg whites, and egg yolks in egg whites frozen, refrigerated liquid, or dried forms)?

- Whole eggs including yolks
- Egg whites
- Egg substitutes

If you consume eggs, what is your primary method of cooking?

- Grilling
- Pan or shallow frying
- Deep-frying
- Baking
- Other

How often do you consume a serving of eggs?

- <1 time per week
- 1-2 times per week
- 3-4 times per week
- 5-6 times per week
- 1 time per day
- 2-3 times per day
- 4-5 times per day
- 6 or more times per day

### **Meat Alternatives**

For this question, please estimate the frequency and quantity of the item in question. Frequency is estimated as: 1-2 times per week, 3-4 times per week, 5-6 times per week, 1 time per day, 2-3 times per day, 4-5 times per day, 6 or more times per day.

Please quantify intake in terms of servings. The following is an example of 1 SERVING of meat alternatives: 1/2 cup raw/cooked tofu (or alternative).

Please choose only one answer for each question.

Do you consume meat alternatives (tempeh, tofu, seitan, gluten, etc)?

- No
- Yes

How often do you consume a serving of meat alternatives (tempeh, tofu, seitan, gluten, etc)?

- <1 time per week
- 1-2 times per week
- 3-4 times per week
- 5-6 times per week
- 1 time per day
- 2-3 times per day
- 4-5 times per day
- 6 or more times per day

### **Yoghurt & Cheese**

For this question, please estimate the frequency and quantity of the item in question. Frequency is estimated as: 1-2 times per week, 3-4 times per week, 5-6 times per week, 1 time per day, 2-3 times per day, 4-5 times per day, 6 or more times per day.

Please quantify intake in terms of servings. The following are examples of 1 SERVING of yoghurt and/or cheese: 1 cup yoghurt/cheese; 8 fluid oz yoghurt/cheese).  
Please choose only one answer for each question.

Do you consume yoghurt and/or cheese?

- No
- Yes

If you consume yoghurt and/or cheese, what type do you typically eat?

- Whole fat cheese or yoghurt
- Low fat cheese or yoghurt
- 2% cheese or yoghurt
- Non-fat cheese or yoghurt
- Cottage cheese

How often do you consume a serving of yoghurt and/or cheese?

- <1 time per week
- 1-2 times per week
- 3-4 times per week
- 5-6 times per week
- 1 time per day
- 2-3 times per day
- 4-5 times per day
- 6 or more times per day

### **Sweets & Desserts**

For this question, please estimate the frequency and quantity of the item in question. Frequency is estimated as: 1-2 times per week, 3-4 times per week, 5-6 times per week, 1 time per day, 2-3 times per day, 4-5 times per day, 6 or more times per day.

Please quantify intake in terms of servings. The following are examples of 1 SERVING of dessert: 1 oz serving; OR 100g serving; OR 1 2" brownie; OR 1/2 cup ice-cream.

Please choose only one answer for each question.

Do you consume sweets, baked goods and/or desserts?

- No
- Yes

If you consume sweets, baked goods and/or desserts, what type do you typically eat?

- Ice-cream
- Cakes and cookies and brownies
- Muffins
- Pies
- Doughnuts

How often do you consume a serving of sweets, baked goods and/or desserts?

- <1 time per week
- 1-2 times per week
- 3-4 times per week
- 5-6 times per week
- 1 time per day
- 2-3 times per day
- 4-5 times per day
- 6 or more times per day

## Appendix 4: Memory Card for Patients while on Study

This is a questionnaire to facilitate self-monitoring of symptoms that may be related to the fecal microbiome transplant (FMT) and/or pembrolizumab therapy that you have received. You should review this questionnaire daily while on study. If you do develop symptoms, particularly if these symptoms are persistent, please bring this to the attention of the investigator and your study nurse. This questionnaire will be administered at each study visit.

Memory Card					
Adverse Event	1	2	3	4	5
Abdominal discomfort	Asymptomatic; clinical or diagnostic observations only; intervention not indicated	Symptomatic; limiting instrumental ADL	Severe discomfort; limiting self care ADL	N/A	N/A
Constipation	Occasional or intermittent symptoms; occasional use of stool softeners, laxatives, dietary modification, or enema	Persistent symptoms with regular use of laxatives or enemas; limiting instrumental ADL	Obstipation with manual evacuation indicated; limiting self care ADL	Life-threatening consequences; urgent intervention indicated	N/A
Diarrhea	Increase of <4 stools per day over baseline; mild increase in ostomy output compared to baseline	Increase of 4 - 6 stools per day over baseline; moderate increase in ostomy output compared to baseline	Increase of $\geq 7$ stools per day over baseline; incontinence; severe increase in ostomy output compared to baseline; limiting self care ADL	Life-threatening consequences; urgent intervention indicated	N/A
Fever	38.0-39.0 degrees C (100.4-102.2 degrees F)	>39.0-40.0 degrees C (102.3-104.0 degrees F)	>40.0 degrees C (> 104.0degrees F) for $\leq 24$ hrs	>40.0 degrees C (> 104.0degrees F) for >24 hrs	N/A
Flatulence	Asymptomatic; clinical or diagnostic observations only; intervention not indicated	Symptomatic; limiting instrumental ADL	Severe discomfort; limiting self care ADL	N/A	N/A
Vomiting	1 - 2 episodes (separated by 5minutes) in 24 hrs	3 - 5 episodes (separated by 5minutes) in 24 hrs	$\geq 6$ episodes (separated by 5minutes) in 24 hrs; tube feeding, TPN or hospitalization indicated	Life-threatening consequences; urgent intervention indicated	N/A

## Appendix 5: Dose Modifications for Pembrolizumab for Immune-Related Adverse Events

Adverse events (AEs) associated with pembrolizumab exposure may represent an immunologic etiology. These immune-related AEs (irAEs) may occur shortly after the first dose or several months after the last dose of pembrolizumab treatment and may affect more than one body system simultaneously. Therefore, early recognition and initiation of treatment is critical to reduce complications. Based on existing clinical study data, most irAEs were reversible and could be managed with interruptions of pembrolizumab, administration of corticosteroids, and/or other supportive care. For suspected irAEs, ensure adequate evaluation to confirm etiology or exclude other causes. Additional procedures or tests such as bronchoscopy, endoscopy, or skin biopsy may be included as part of the evaluation. Based on the severity of irAEs, withhold or permanently discontinue pembrolizumab and administer corticosteroids. Dose modification and toxicity management guidelines for irAEs associated with pembrolizumab are provided here.

**Table 5-1: Dose Modification Guidelines for Drug-related Adverse Events: Pembrolizumab**

General instructions:				
1. Corticosteroid taper should be initiated upon AE improving to Grade 1 or less and continue to taper over at least 4 weeks.				
2. For situations where pembrolizumab has been withheld, pembrolizumab can be resumed after AE has been reduced to Grade 1 or 0 and corticosteroid has been tapered. Pembrolizumab should be permanently discontinued if AE does not resolve within 12 weeks of last dose or corticosteroids cannot be reduced to $\leq 10$ mg prednisone or equivalent per day within 12 weeks.				
3. For severe and life-threatening irAEs, IV corticosteroid should be initiated first followed by oral steroid. Other immunosuppressive treatment should be initiated if irAEs cannot be controlled by corticosteroids.				
irAE	CTCAE Grade	Action Taken with Pembrolizumab	irAE Management with Corticosteroid and/or Other Therapies	Monitoring and Follow-Up
Pneumonitis	Grade 2	Withhold	Administer corticosteroids (initial dose of prednisone 1-2 mg/kg or equivalent) followed by taper.	Monitor subjects for signs and symptoms of pneumonitis. Evaluate subjects with suspected pneumonitis with radiographic imaging and initiate corticosteroid treatment. Add prophylactic antibiotics for opportunistic
	Grade 3 or 4, or recurrent Grade 2	Permanently discontinue		

				infections
Diarrhea/colitis	Grade 2 or 3	Withhold	Administer corticosteroids (initial dose of prednisone 1-2 mg/kg or equivalent) followed by taper.	Monitor subjects for signs and symptoms of enterocolitis (ie, diarrhea, abdominal pain, blood or mucus in stool with or without fever) and of bowel perforation (ie, peritoneal signs and ileus). Subjects with $\geq$ Grade 2 diarrhea suspecting colitis should consider GI consultation and performing endoscopy to rule out colitis. Subjects with diarrhea/colitis should be advised to drink liberal quantities of clear fluids. If sufficient oral fluid intake is not feasible, fluid and electrolytes should be substituted via IV infusion. Consider infliximab 5 mg/kg for treatment of severe immune-related colitis that does not respond within 1 week to high-dose steroids.
	Grade 4	Permanently discontinue		
AST/ALT elevation or increased bilirubin	Grade 2	Withhold	Administer corticosteroids (initial dose of prednisone 0.5-1 mg/kg or equivalent)	Monitor with liver function tests (consider weekly or more frequently until liver enzyme value returned to

			followed by taper.	baseline or is stable).
	Grade 3 or 4	Permanently discontinue	Administer corticosteroids (initial dose of prednisone 1-2 mg/kg or equivalent) followed by taper.	
T1DM or hyperglycemia	New onset T1DM or Grade 3 or 4 hyperglycemia associated with evidence of $\beta$ -islet failure	Withhold	Initiate insulin replacement therapy for subjects with T1DM.  Administer antihyperglycemic in subjects with hyperglycemia.	Monitor subjects for hyperglycemia or other signs and symptoms of diabetes.
Hypophysitis	Grade 2	Withhold	Administer corticosteroids and initiate hormonal replacements as clinically indicated.	Monitor for signs and symptoms of hypophysitis (including hypopituitarism and adrenal insufficiency).
	Grade 3 or 4	Withhold or permanently discontinue		
Hyperthyroidism	Grade 2	Withhold	Treat with nonselective beta-blockers (eg, propranolol) or thionamides as appropriate.	Monitor for signs and symptoms of thyroid disorders.
	Grade 3 or 4	Withhold or permanently discontinue a, b		
Hypothyroidism	Grade 2-4	Continue	Initiate thyroid replacement hormones (eg, levothyroxine or liothyronine) per standard of care.	Monitor for signs and symptoms of thyroid disorders.

Nephritis and renal dysfunction	Grade 2	Withhold	Administer corticosteroids (initial dose of prednisone 1-2 mg/kg or equivalent) followed by taper.	Monitor changes of renal function.
	Grade 3 or 4	Permanently discontinue		
Rash	Grade 1 or 2	Continue	Manage with topical steroids with or without drug interruption	Restart pembrolizumab at same dose if rash is mild and assessed as Grade 3 based only on body surface area and resolves without oral steroids. If oral steroids are required, or if rash is severe, decrease by 1 dose level once resolved to Grade 0-1.
	Grade 3 c	Withhold until toxicity resolves to Grade 0-1	Administer corticosteroids (initial dose of prednisone 1-2 mg/kg or equivalent) followed by taper.	
	Grade 4	Permanently discontinue		
Amylase and/or lipase increased.	Grade 3 or less	May continue treatment with approval of PI or medical monitor		Permanently discontinue if clinical signs and symptoms of pancreatitis develop (abdominal pain, nausea, vomiting).
	Grade 4	Withhold until toxicity resolves to Grade 0-1 d .		
Myocarditis	Grade 1 or 2	Hold therapy till toxicity resolves to Grade 0	Admit patient and start high-dose corticosteroids.	Intensive care unit admission; consider other immunosuppressants if the patient's condition deteriorates.
	Grade 3 or 4	Permanently discontinue		
Neuropathy	Grade 2	Toxicity resolves to ≤ Grade 1 or		

		baseline within 4 weeks, restart at same dose. Toxicity does not resolve to $\leq$ Grade 1 within 4 weeks, reduce dose 1 dose level.		
	Grade 3 or 4	Permanently discontinue		
All other immune-related AEs	Grade 3, or intolerable/persistent Grade 2	Withhold	Based on severity of AE administer corticosteroids.	Ensure adequate evaluation to confirm etiology or exclude other causes.
	Grade 4 or recurrent Grade 3.	Permanently discontinue		

AE = adverse event; ALT = alanine aminotransferase; AST = aspartate aminotransferase; GI = gastrointestinal; irAE = immune-related adverse event; IV = intravenous; T1DM = Type 1 diabetes mellitus.

aDecision to withhold or permanently discontinue pembrolizumab is at the discretion of the investigator or treating physician.

bFor subjects with Grade 3 or 4 immune-related endocrinopathy where pembrolizumab must be withheld, pembrolizumab may be resumed when AE resolves to  $\leq$  Grade 2 and is controlled with hormonal replacement therapy or achieved metabolic control (in case of T1DM).

cParticipants with Grade 3 rash in the absence of desquamation, with no mucosal involvement, not requiring systemic steroids, and resolving to Grade 1 within 14 days do not have to withhold study treatment.

dIf Grade 4 amylase and/or lipase increase is asymptomatic and abdominal imaging suggests no pathology, study treatment dosing may continue with medical monitor approval.

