### 5.2.1 Dose Selection/Modification (Pembrolizumab)

#### 5.2.1.1 Dose Selection

Pembrolizumab will be dosed at a fixed dose of 200mg every 3 weeks. Rationale for selection of doses to be used in this trial is provided in Section 4.0 – Background and Rationale.

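### Table 5-1 orders a one-level pembrolizumab reduction after steroid-treated or severe rash and for persistent Grade 2 neuropathy, but the trial defines no dose below 200 mg

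*Combined protocol and SAP*

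**What the plan says.** The treatment sections give one pembrolizumab dose. Section 5.2.1.1 states: "Pembrolizumab will be dosed at a fixed dose of 200mg every 3 weeks". Table 5.2-1 and Section 5.2.2 repeat 200 mg every 3 weeks, and none of the three names an alternative.

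Appendix 5, Table 5-1 sets out what to do after drug-related adverse events. Two rows go beyond continuing, withholding or stopping.

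- **Rash.** At Grade 3 the action is "Withhold until toxicity resolves to Grade 0-1", and the management is "Administer corticosteroids (initial dose of prednisone 1-2 mg/kg or equivalent) followed by taper". The follow-up column then sets the restart dose. It says "Restart pembrolizumab at same dose if rash is mild and assessed as Grade 3 based only on body surface area and resolves without oral steroids", and otherwise "If oral steroids are required, or if rash is severe, decrease by 1 dose level once resolved to Grade 0-1". Footnote c exempts from withholding those Grade 3 rashes without desquamation, "with no mucosal involvement, not requiring systemic steroids, and resolving to Grade 1 within 14 days do not have to withhold study treatment". Grade 4 rash means permanent discontinuation.
- **Neuropathy, Grade 2.** If the event falls to Grade 1 or lower or returns to "baseline within 4 weeks, restart at same dose". If it has not reached "Grade 1 within 4 weeks, reduce dose 1 dose level". Grade 3 or 4 means permanent discontinuation.

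**The concern.** A reduction by one level needs a ladder of at least two levels, and this protocol has one. An investigator whose patient meets either trigger cannot find the next dose in the protocol. The choices are to give 200 mg against the row, to make up a dose, or to stop treatment. Two patients with the same event could be handled differently.

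Neuropathy is the more awkward case. Read literally, the cell answers an unresolved Grade 2 event with a smaller dose and no interruption, which could be taken as dosing through toxicity. What is at stake is consistent and safe handling of individual patients, not the trial's inference.

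**Working it through.** There is no stated figure to reproduce. The check sets every mention of pembrolizumab dose, dose level and dose change side by side.

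**Is a lower level defined anywhere?**

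- Table 5.2-1 and Sections 5.2.1.1 and 5.2.2: 200 mg every 3 weeks only.
- Section 5.2.1.2, the dose-modification section: withholding, discontinuation, and a conditional continuation for certain laboratory events. No reduction step.
- Introduction to Appendix 5: withhold or permanently discontinue. No reduction step.
- Appendix 6: the only halving is of the infusion rate after a Grade 2 infusion reaction, not of the dose.
- Section 4.2.2: the dose levels of 1, 3 and 10 mg/kg every 2 weeks belong to an earlier Phase I trial given as background. They are weight-based and on another schedule, so they are not steps down from a fixed 200 mg. The rest of the section argues for 200 mg and offers nothing below it.
- Table 7.2.4-1, rechallenge entry: Sponsor approval follows the protocol's dose modification guidelines, which leads back to Table 5-1.

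Result: dose levels defined, 1; lower levels defined, 0.

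**How much of Table 5-1 is affected?** The event rows are pneumonitis; diarrhea/colitis; AST/ALT or bilirubin; T1DM/hyperglycemia; hypophysitis; hyperthyroidism; hypothyroidism; nephritis; rash; amylase/lipase; myocarditis; neuropathy; and all other immune-related events. That is 13. Rash and neuropathy name a dose level, so 2 of 13 are affected and 13 - 2 = 11 use only continue, withhold (or hold) and discontinue.

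**Which patients reach the undefined step?**

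- *Rash.* Grade 1-2 continues and Grade 4 stops, so the reduction concerns Grade 3. Two kinds of Grade 3 rash escape it: the footnote c cases, which need no withholding, and mild rash graded 3 on body surface area alone that resolves without oral steroids, which restarts at the same dose. Otherwise the row's own management is prednisone 1-2 mg/kg or equivalent, which ordinarily meets the oral-steroid trigger. The undefined branch is therefore the ordinary path for treated Grade 3 rash. Everything before the restart is defined.
- *Neuropathy.* Grade 2 that settles within 4 weeks restarts at the same dose, which is clear. Grade 2 that does not settle meets the undefined reduction in the action column itself. The word restart in the first branch implies an interruption, but the cell never orders one. By contrast, the row for all other immune-related events withholds for intolerable or persistent Grade 2.

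**Do existing rules supply an answer?** General instruction 2 lets withheld pembrolizumab resume once the event is at Grade 0-1 and corticosteroid has been tapered, and requires permanent discontinuation if the event has not resolved within 12 weeks of the last dose. Section 5.2.1.2 has a similar 12-week limit. These rules would work for both events, but the specific rows say something else, and neither rule tells the investigator to disregard them.

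**The case against.** The best defence is that this is leftover template wording that a sensible reader would pass over. Section 5.6.1 describes the table's supportive care as suggested, its title calls it guidelines, and the mandatory wording in Section 5.2.1.2 is to withhold. With one fixed dose and a general instruction on resumption, the intended handling can be guessed. Rechallenge after a serious event possibly caused by pembrolizumab, or where re-exposure adds significant risk, also needs advance Sponsor approval, so in those cases the investigator does not decide alone.

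Much of that stands, and it limits the point to two cells. It does not remove it: a specific row normally prevails over a general instruction, not every Grade 3 rash is serious, and Sponsor approval does not supply a dose.

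Several stronger readings are tempting, but the documents do not support them.

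- A reader might infer that the rash rules as a whole fail. They do not; withholding, steroids and the Grade 4 stop are all defined.
- A reader might infer from Section 5.2.1.2, which cites a Table 7-1, that a dose-level table has gone missing. The citation points expressly to Appendix 5, so it looks like a numbering slip for Table 5-1. Appendix 6 has a similar slip.
- A reader might cite Section 7.1.5.7, where retreatment is at the same dose, as a further contradiction. That section covers a second course after a complete response or 24 months of treatment, not restart after an adverse event.
- A reader might infer that general instruction 2 clashes with the Grade 2 laboratory exception in Section 5.2.1.2. The main text states that exception explicitly, so the two can be followed together.

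**Conclusion.** The point holds as a minor internal inconsistency that bears on patient safety. Two of 13 event rows order a reduction to a level that does not exist. For rash the gap is the restart dose alone; for neuropathy it is the action.

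The conclusion rests on the text as it stands. The dose table, Section 5.2.1.2 and both rows are present and legible, and nothing suggests that a dose ladder was blacked out or lost. The documents give no rates for steroid-treated Grade 3 rash or persistent Grade 2 neuropathy, so the number of the planned 20 patients who would meet the gap cannot be estimated from them.

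A reader might infer that undefined dosing weakens the efficacy conclusion. The documents do not support that: the two-stage rule counts RECIST responses among evaluable patients, evaluability does not depend on the restart dose, and the 5% and 25% response rates, the 0.07 significance level, the 90% power and the sample size of 13 plus 7 do not change.

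**What to change.** Delete both dose-level reductions and apply general instruction 2 in their place. For steroid-treated or severe Grade 3 rash, and for Grade 2 neuropathy:

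- withhold pembrolizumab, stating this explicitly in the neuropathy cell;
- resume at 200 mg only at Grade 0-1 (or baseline, for neuropathy) with corticosteroid tapered;
- permanently discontinue if not resolved within 12 weeks of the last dose.

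Keep the Grade 4 rash rule, the Grade 3-4 neuropathy rule, footnote c, the sentence on mild rash graded by body surface area alone, and the Section 5.2.1.2 rule to stop when a severe event recurs on re-challenge.

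The cost is protocol text only, in two table cells. There is a clinical trade-off: the rows were evidently meant to treat these cases more cautiously than milder ones, and full-dose resumption removes that. If the sponsor wants to keep the extra caution, permanent discontinuation in these two situations is an equally workable instruction. Either choice can be followed; the present wording cannot.
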